7.6.5. Vital Signs

Descriptive statistics for each vital sign (e.g. systolic blood pressure, diastolic blood pressure, pulse rate, body temperature, respiratory rate, height, weight, body mass index) will be summarized at scheduled visits. Summaries will include actual values and changes from baseline.

Vital sign measurements will be presented for each patient in a data listing, with abnormal vital signs flagged.

7.6.6. Electrocardiogram

For electrocardiogram (ECG) parameters, these will be summarized using descriptive statistics for actual values and for changes from baseline by scheduled time of evaluation. The number and percentage of patients with normal, abnormal, and clinically significant abnormal results at baseline and each timepoint will be summarized. For assessments where ECG is performed in triplicate, the average of the 3 (or all available) readings will be used for analysis

ECG findings will include rhythm, ventricular rate, PR interval, QRS duration, QT interval, and corrected QT interval (QTc).

Corrected QT interval, if not collected, will be calculated using Fridericia's correction formula.

Fridericia's cube-root corrected QT: QTcF (ms) = QT (ms) $\times \sqrt[3]{\frac{HR(bpm)}{60}}$.

Baseline, post baseline maximum QTcF and post baseline maximum change from baseline in QTcF during the study will be summarized with descriptive statistics. The incidence of notable ECG changes from baseline in maximum absolute QT_cF , intervals (<=450, > 450, > 480, and > 500 ms) over all post-treatment evaluations, as well as in QTcF, maximum changes from baseline (<=30 ms, > 30 -60 ms and > 60 ms) over all post-treatment evaluations will be summarized. A listing of all ECG data will be provided.

7.6.7. Physical Examination Findings

Physical examinations will be conducted throughout the study. If any abnormalities are observed during these physical exams, then this will be recorded on the adverse event form.

A separate listing per patient will be generated to display the date and time of the physical exam.

7.7. Anti-Drug Antibody

Patients with treatment-induced ADA will be placed in the treatment emergent ADA positive group for the calculation of ADA incidence. Treatment induced ADA is defined as ADA developed de novo (seroconversion) after drug administration (i.e., formation of ADA at any time after the initial drug administration in patients without pre-existing ADA)

The number and associated percentage of patients who are ADA positive at baseline and at any post-baseline visit will be summarized by treatment group. A listing of patients with positive ADA assay results and corresponding titers will be provided along with the ADA results. Circulating Immune Complexes (CIC) and anti-GdIgA1 antibody will be summarized descriptively by visit as appropriate and the corresponding listing will be provided.

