2. STUDY OVERVIEW

2.1. Study Design

This study is a multicenter, double-blind, placebo-controlled study comprised of three periods (Figure 1). Eligible patients will begin a 14-week observational run-in period during which treatment with the standard of care is expected to remain unchanged. At the end of run-in period, patients whose average urine protein (UP) of two valid urine collections is at or higher than 1g/24-h are eligible for randomization into the 36-week double blind (DB) period. Approximately 30 patients are planned to be randomized in a 2:1 ratio, 20 in the cemdisiran arm and 10 in the placebo arm in the DB period, which is followed by a 156-week open-label extension (OLE) period to further evaluate the long-term safety and efficacy. All patients will be followed for safety for 52 weeks after the end of study visit.

The independent Data Monitoring Committee (DMC) will have access to subject level treatment assignments and perform periodic reviews of unblinded data throughout. Details are provided in the DMC Charter of the study.

Figure 1 Study Design

days)	Run-in Period (14 Weeks)		Treatment 1 (36 Wee	Freatment Period (36 Weeks)		sment	Open-label Extension (156 Weeks)		iod	
Screening (up to 120 c	Standard of care	mization (2:1	ALN-CC5 600mg Q4W (n=20) + Standard of care)T k 32)	S ¢ 36)	ndpoint asses	ALN-CC5	DT (c 184) 0S (s 188)	SS (188)	ty Follow-up (2 Weeks)
		Rando	Placebo (n=10) + Standard of care	EC (Wee	EC (Wee	Primary e	+ Standard of care	EC (Week	EC (Week	Safe (5

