 To assess the incidence of antidrug antibodies (ADA) 	 Change from baseline in the urine albumin/creatinine ratio (UACR) as measured in 24-hour urine at Week 32 Change from baseline in C5 level over the course of the study Change from baseline in complement activity (Complement Alternative Pathway [CAP] and Complement Classical Pathway [CCP]) over the course of the study Evaluation of area under the curve (AUC), maximum plasma concentration (Cmax), time to maximum plasma concentration (Tmax), terminal half-life (t½), clearance (CL/F), volume of distribution (V/F), cumulative amount excreted unchanged in urine (Ae) and percent of dose excreted in the urine (fe) of cemdisiran (25-mer) and 23-mer Evaluation of AUC, Cmax, Tmax, t½, CL/F, V/F, Ae and fe of 22-mer AS(N-1)3' Change from baseline in levels of renal damage, complement activation and inflammation markers over the course of the study Incidence of antidrug antibodies (ADA)

4. **PATIENT POPULATION**

4.1. **Population Definitions**

The following patient populations will be used for analyses:

- Modified Intent-to-Treat Analysis Set (mITT): All patients who receive any amount of study drug and have baseline and at least one post-baseline 24-hour urine protein creatinine ratio assessment. Patients will be grouped by assigned treatments (i.e., as randomized).
- Safety Analysis Set: All patients who receive any amount of study drug. Patients will be analyzed according to the treatment actually received.

- PK Analysis Set: All patients who receive a full dose of study drug and have at least 1 PK concentration measurement.
- PD Analysis Set: All patients who receive a full dose of study drug and who have at least one post-dose blood sample for the determination of plasma C5 level.
- All Cemdisiran Treated Set: All patients who received at least one dose of cemdisiran, including patients who took cemdisiran during the DB period and patients who first took placebo during the DB period and switched to cemdisiran during the OLE period.

The primary population used to evaluate efficacy will be the mITT Population unless stated otherwise. Safety during the DB period will be analyzed using the Safety Analysis Set. The PK and PD Analysis Sets will be used to conduct PK and PD analyses, respectively. The All Cemdisiran Treated Set will be used to summarize long-term efficacy and safety of cemdisiran.

4.2. **Protocol Deviations**

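### Treatment-emergent ADA incidence counts de novo antibody only, so a baseline-positive patient whose titer rises on cemdisiran is left out of that figure

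*SAP*

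**What the plan says.** Section 7.7 of the current SAP gives one route into the numerator: "Patients with treatment-induced ADA will be placed in the treatment emergent ADA positive group for the calculation of ADA incidence". It then fixes what counts: "Treatment induced ADA is defined as ADA developed de novo (seroconversion) after drug administration", explained as "formation of ADA at any time after the initial drug administration in patients without pre-existing ADA". It names no treatment-boosted category, no titer-rise criterion and no denominator.

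The same section plans two further outputs. One is a table: "The number and associated percentage of patients who are ADA positive at baseline and at any post-baseline visit will be summarized by treatment group". The other is a listing: "A listing of patients with positive ADA assay results and corresponding titers will be provided along with the ADA results". No rule in the section makes use of the titers.

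Section 3 lists the "incidence of antidrug antibodies" among the objectives and endpoints. In the current Table 1 the tier headings are not legible in the text at hand. In the preceding SAP version the same item stands under the exploratory tier. Section 5.5 says that all comparisons are descriptive.

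The two preceding SAP versions had only the baseline and post-baseline summary with listings. The de novo definition appears only in the current one.

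**The concern.** An immune response to the drug can show itself in two ways: new antibody in a patient who had none, or a rise in antibody that was already there. The rule in Section 7.7 counts the first and excludes the second, however large the rise. This is a stated rule and not a matter left open, so a programmer following it would have to leave the boosted patient out.

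It also sits oddly with the SAP's own idea of treatment emergence. Section 7.6 treats an adverse event as treatment-emergent if it begins or gets worse after first dose. For ADA, a worsening of a pre-existing state is excluded, and no reason is given.

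At stake is one descriptive rate in a small trial, where a single patient moves the figure visibly. If the titer criterion is not set beforehand, any judgement that a patient was boosted will be made from the listing after the titers have been seen.

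**Working it through.** **Inputs**

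- Definition of the numerator: Section 7.7, as quoted above.
- Arm sizes: Section 2.1, "Approximately 30 patients are planned to be randomized in a 2:1 ratio, 20 in the cemdisiran arm and 10 in the placebo arm". This gives N = 20 on cemdisiran in the double-blind period, and at most 20 + 10 = 30 exposed to cemdisiran if every placebo patient switches.
- Baseline ADA prevalence and boosting rate: not given, so the counts below are assumptions for illustration.

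The SAP states no ADA rate, so there is no figure of its own to reproduce.

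**Notation.** d = patients with de novo ADA; p = patients positive at baseline; b = those among the p whose titer rises after dosing (b ≤ p).

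**Formulas, with all N patients as denominator**

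- Treatment-emergent incidence under Section 7.7: d/N
- Incidence counting induced or boosted: (d + b)/N
- Shortfall: b/N
- Positive at any post-baseline visit, if all baseline positives stay positive: (d + p)/N

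**Shortfall**

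| b | N = 20 | N = 30 |
|---|---|---|
| 0 | 0 | 0 |
| 1 | 1/20 = 5.0 points | 1/30 = 3.3 points |
| 2 | 2/20 = 10.0 points | 2/30 = 6.7 points |

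**Can the planned tables reveal b?** Take N = 20, d = 1, p = 2 and let b vary:

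| b | Section 7.7 incidence | Baseline positive | Any post-baseline positive | Induced or boosted |
|---|---|---|---|---|
| 0 | 1/20 = 5.0% | 2/20 = 10.0% | 3/20 = 15.0% | 1/20 = 5.0% |
| 1 | 1/20 = 5.0% | 2/20 = 10.0% | 3/20 = 15.0% | 2/20 = 10.0% |
| 2 | 1/20 = 5.0% | 2/20 = 10.0% | 3/20 = 15.0% | 3/20 = 15.0% |

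The three planned figures are identical in every row, while the induced-or-boosted incidence runs from 5.0% to 15.0%. The tables bracket the answer, between d/N and (d + p)/N, but do not give it.

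**Denominator.** Because the definition applies only to patients without pre-existing ADA, one analyst could divide by N and another by N − p. With d = 1 and p = 2 that is 1/20 = 5.0% or 1/18 = 5.6%. The SAP does not say which. The statement that the incidence can only be too low holds for a common denominator N.

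**The case against.** The strongest reply is that the information is not lost. A boosted patient appears in the baseline-positive row and in the any-post-baseline row, and every positive result is listed with its titer. With about 30 patients, a reader can go through that listing by hand. This stands as far as it goes: what is missing is a rule and a summary row, not data. It does not answer the point that the headline incidence excludes these patients by definition, or that the listing comes with no criterion for reading it.

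The second reply is that ADA incidence is exploratory and descriptive, and no primary or secondary conclusion depends on it. That also stands, and it sets the weight of the point.

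Three stronger readings are tempting, and the document does not support them:

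- A reader might infer that immunogenicity *is* understated. That requires at least one baseline-positive patient with a rising titer, and nothing in the SAP shows that one is expected.
- A reader might infer that boosted patients would contaminate comparisons of adverse events, C5 or PK by ADA status. The SAP plans no such comparison. Sections 7.4 and 7.6 summarize by arm or treatment sequence, Section 7.5 summarizes PK by time point, and Section 7.1.2 does not name ADA status as a subgroup.
- A reader might want an expected number of missed patients from an assumed prevalence of pre-existing ADA. The SAP gives no prevalence, and prevalence would in any case describe baseline positivity and not boosting.

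For placebo patients who switch, Section 5.3 already redefines baseline as the last assessment before the first cemdisiran dose, with exceptions only for 24-hour urine and ECG. There is no gap there beyond a missing cross-reference.

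**Conclusion.** The point holds in conditional form. As written, the treatment-emergent ADA incidence omits any baseline-positive patient whose titer rises on cemdisiran, and no planned table can identify that patient. With all patients in the denominator, the understatement is 5.0 points per boosted patient at N = 20 and 3.3 points at N = 30, and zero if there are none. The N = 30 figure assumes full planned enrolment and that every placebo patient switches. How many boosted patients to expect cannot be derived from the SAP. The point is minor, because the endpoint is exploratory and descriptive and the underlying results are tabulated and listed. It is worth making because the correction is specific and nearly free.

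**What to change.** In Section 7.7:

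1. Define treatment-emergent ADA as treatment-induced or treatment-boosted.
2. Define boosted as positive at baseline with a post-dose titer above the baseline titer by a prespecified factor. Take the factor from the assay's dilution scheme, which the SAP does not give, and fix it before titers are reviewed.
3. Report induced, boosted and total as separate rows, and state the denominator of each.
4. For patients who switch from placebo, refer pre-existing ADA to the redefined baseline in Section 5.3.

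The cost is a few sentences and extra table rows. Titers are already collected and listed, so no new data are needed. The reported incidence stays the same or rises, on a common denominator.

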7.8. COVID-19 Pandemic Impact Analyses

Additional data were collected to characterize the impact of the COVID-19 pandemic on study conduct as shown in Appendix 10.1.

7.8.1. General Impact

Patients who discontinue treatment or stop study participation due to COVID-19 as assessed in the COVID-19 Data Collection Instrument will be included in patient disposition summaries.

Impact on study participation due to COVID-19 pandemic, including visit(s) missed, delayed, partially completed, completed, location changes (telehealth, local labs, other sites), study drug dosing missed or delayed will be summarized overall on the patient level, and overall and by visit on the event level. Visit and dosing delays can be defined by time windows specified by the protocol before the pandemic and the relaxed windows in responding to the pandemic in Amendment 4 (dated 19 January, 2021).

7.8.2. Impact on Efficacy

A summary of missing data for primary and secondary efficacy endpoints due to COVID-19 pandemic will be provided. Specifically, the number and percent of patients in each treatment arm with missing data in 24h UPCR/24h UP, spot UPCR, and hematuria by microscopic examination and urine dipstick at each scheduled assessment visit will be presented. Missing efficacy data due to Covid-19 could be identified by if the visit associated with the assessment is missed (Appendix 10.1).

For primary and secondary efficacy endpoints, the number and percentage of patients with outof-window visits based on the original protocol at each scheduled visit will be summarized.

7.8.3. Impact on Adverse Events

The number and percent of patients with AEs mapped to COVID-19 custom query by HLT and PT will be presented for overall and by treatment.

7.8.4. Other Impacts

Protocol deviation due to the COVID-19 pandemic will be summarized and will be indicated in the listing of protocol deviation. AEs, study drug exposure, and efficacy listings will include identification of assessments occurring during the pandemic. For patients reporting an AE mapped to the COVID-19 custom query, AEs and prior and concomitant medications will also be presented in separate data listings.

Change from SAP Amendment 1.0	Detailed Description/Rationale
5.8 Analysis Cutoff and Database Lock	Removed wording of Week 36 primary CSR as there will be no CSR for the Week 36 primary analysis.
6.4 Drug Exposure	Summary for the All Cemdisiran Treated Set added.
7.1 Primary Endpoint	Plots for summary of 24-hour UPCR in original and log scale added.
	Summary for long term efficacy using the all cemdisiran treated set added.
7.1.2 Subgroup Analysis	Added Race (Asian vs. non-Asian) to the list of subgroups.

GM	Geometric mean			
HLT	High level term			
IgAN	Immunoglobulin A nephropathy			
IRS	Interactive Response System			
ISR	Injection site reactions			
ITT	Intent-to-Treat Analysis Set			
LLN	Lower Limit of Normal			
LLOQ	Lower limit of quantification			
MAC	Membrane attack complex			
MedDRA	Medical Dictionary for Regulatory Activities			
OLE	Open-label extension			
РК	Pharmacokinetic(s)			
PD	Pharmacodynamic			
PT	Preferred Term			
RAS	Renin-angiotensin system			
RBC	Red blood cell			
RNAi	RNA interference			
SAF	Safety Analysis Set			
SAP	Statistical analysis plan			
SOC	System Organ Class			
TEAEs	Treatment emergent adverse events			
UACR	Urine albumin:creatinine ratio			
ULN	Upper limit of normal			
ULOO	Upper limit of quantification			

Abbreviation	Definition
UP	Urine Protein
UPCR	Urine protein:creatinine ratio
WHO-DRL	WHO Drug Dictionary

1. INTRODUCTION

Immunoglobulin A nephropathy (IgAN) is the most common form of primary glomerulonephritis and can progress to renal failure.

The clinical presentation of IgAN is highly variable, ranging from asymptomatic microscopic hematuria to a rapidly progressive form of glomerulonephritis. The therapeutic options are limited and include nonspecific treatment to reduce blood pressure and proteinuria by reninangiotensin system (RAS) blockade. No disease-specific therapies are currently available, and an unmet need persists for disease-modifying interventions.

Cemdisiran is an investigational RNA interference (RNAi) therapeutic designed to suppress liver production of C5 protein, resulting in inhibition of terminal complement pathway activity and prevention of membrane attack complex (MAC) formation and C5a release. This inhibition would be expected to reduce mesangial cell proliferation and tissue injury in patients with IgAN, resulting in reduced renal injury. Both lectin and alternative pathways of complement have been implicated in IgAN pathology. Cemdisiran-mediated silencing of C5 will inhibit MAC formation and C5a release regardless of the activating pathway. This approach is particularly appealing in IgAN where the relative contribution of the different complement pathways may vary between patients.

Study ALN-CC5-005 is a Phase 2 study to evaluate the efficacy and safety of cemdisiran in the treatment of patients with IgAN. This statistical analysis plan (SAP) has been developed based on the Protocol Amendment 4 dated 19 January 2021. Any change to the data analysis methods described in the protocol, as well as the justification for the change, will be described in the SAP (Section 8).

2. STUDY OVERVIEW

2.1. Study Design

This study is a multicenter, double-blind, placebo-controlled study comprised of three periods (Figure 1). Eligible patients will begin a 14-week observational run-in period during which treatment with the standard of care is expected to remain unchanged. At the end of run-in period, patients whose average urine protein (UP) of two valid urine collections is at or higher than 1g/24h are eligible for randomization into the 36-week double blind (DB) period. Approximately 30 patients are planned to be randomized in a 2:1 ratio, 20 in the cemdisiran arm and 10 in the placebo arm in the DB period, which is followed by a 156-week open-label extension (OLE) period to further evaluate the long-term safety and efficacy. All patients will be followed for safety for 52 weeks after the end of study visit.

The independent Data Monitoring Committee (DMC) will have access to subject level treatment assignments and perform periodic reviews of unblinded data throughout. Details are provided in the DMC Charter of the study.

Figure 1 Study Design

days)	Run-in Period (14 Weeks) Treatment Period (36 Weeks)		sment	Open-label Exten (156 Wee	sion Per ks)	iod				
Screening (up to 120 c	Standard of care	mization (2:	ALN-CC5 600mg Q4W (n=20) + Standard of care	DT k 32)	S \$ 36)	S ¢ 36)	ndpoint asses	ALN-CC5	DS ¢ 188)	t 188) ty Follow-up 2 Weeks)
	Statuard of Care	Rande	Placebo (n=10) + Standard of care	E((Wee	E((Wee	Primary e	+ Standard of care	E((Weel	E((Weel	Safe ()

2.2. Randomization Methodology

At the end of run-in period, patients will be randomized 2:1 to the cemdisiran or placebo arms upon confirmation of eligibility using the Interactive Response System (IRS), followed by vaccination against meningococcal infections. Randomization will be carried out by the permuted block randomization stratified by baseline urine proteinuria levels ($\geq 1g/24h$ and < 2g/24h versus $\geq 2g/24h$).

2.3. Blinding and Unblinding

Treatment assignments will be maintained by the IRS. Any unplanned unblinding to investigators or patients occurring during the 36-weeks DB placebo-controlled treatment period will be documented and reported in the Clinical Study Report (CSR).

During the DB treatment period, all subjects will be randomly assigned to cemdisiran or placebo. All site personnel and patients will be blinded to study drug during the DB period. Sponsor personnel will not be blinded to study treatment. Details regarding the blinding aspects during the study are outlined in a Randomization and Blinding Plan for ALN-CC5-005.

2.4. Study Procedures

The schedules of assessments are described in study protocol Table 1 for the DB period and study protocol Table 2 for the OLE period.

3. OBJECTIVE AND ENDPOINTS

The study objectives and endpoints based on the study protocol are presented Table 1 below.

Objectives	Endpoints		
Primary			
• To evaluate the effect of cemdisiran on proteinuria in adult patients with immunoglobulin A nephropathy (IgAN)	• Percent change from baseline in urine protein/creatinine ratio [UPCR] as measured in 24-hour urine at Week 32		
Secondary			
 To evaluate the effect of cemdisiran on additional measures of proteinuria in adult patients with IgAN To evaluate the effect of cemdisiran on hematuria in adult patients with IgAN 	 Percent change from baseline in 24-hour proteinuria (g/24-hours) at Week 32 Percent of patients with partial clinical remission (urine protein [UP] <1.0 g/24-hours) at Week 32 		
• To evaluate the safety and tolerability of cemdisiran	 Percent of patients with >50% reduction in 24-hour proteinuria at Week 32 Change from baseline in UPCR as measured in spot urine at Week 32 Change from baseline in hematuria at Week 32. 		
	• Frequency of adverse events (AEs)		
Exploratory			
 To evaluate the effect of cemdisiran on renal function parameters To evaluate the effect of cemdisiran 	Change from baseline in estimated glomerular filtration rate (eGFR) at Week 32		
on full clinical remission and measures of albuminuria in adult patients with IgAN	• The slope of eGFR computed for the first 36 weeks using all assessments during the period		
 To evaluate the pharmacodynamic (PD) effect of cemdisiran, C5 level and CAP/CCP To characterize the pharmacokinetics 	 The slope of eGFR computed for the entire study period including the open label extension using all assessments during the study. 		
(PK) of cemdisiran and relevant metabolites in plasma and urine in	Change from baseline in creatinine clearance at Week 32		
 adult patients with IgAN To evaluate the effect of cemdisiran on serum and urine markers of 	 Percent of patients in full clinical remission (Urine Protein [UP] <0.3 g/24-hours) at Week 32 		
complement activation, renal damage and inflammation	 Change from baseline in 24-hour albuminuria at Week 32 		

Table 1Objectives and endpoints

 To assess the incidence of antidrug antibodies (ADA) 	 Change from baseline in the urine albumin/creatinine ratio (UACR) as measured in 24-hour urine at Week 32 Change from baseline in C5 level over the course of the study Change from baseline in complement activity (Complement Alternative Pathway [CAP] and Complement Classical Pathway [CCP]) over the course of the study Evaluation of area under the curve (AUC), maximum plasma concentration (Cmax), time to maximum plasma concentration (Tmax), terminal half-life (t½), clearance (CL/F), volume of distribution (V/F), cumulative amount excreted unchanged in urine (Ae) and percent of dose excreted in the urine (fe) of cemdisiran (25-mer) and 23-mer Evaluation of AUC, Cmax, Tmax, t½, CL/F, V/F, Ae and fe of 22-mer AS(N-1)3' Change from baseline in levels of renal damage, complement activation and inflammation markers over the course of the study Incidence of antidrug antibodies (ADA)

4. **PATIENT POPULATION**

4.1. **Population Definitions**

The following patient populations will be used for analyses:

- Modified Intent-to-Treat Analysis Set (mITT): All patients who receive any amount of study drug and have baseline and at least one post-baseline 24-hour urine protein creatinine ratio assessment. Patients will be grouped by assigned treatments (i.e., as randomized).
- Safety Analysis Set: All patients who receive any amount of study drug. Patients will be analyzed according to the treatment actually received.

- PK Analysis Set: All patients who receive a full dose of study drug and have at least 1 PK concentration measurement.
- PD Analysis Set: All patients who receive a full dose of study drug and who have at least one post-dose blood sample for the determination of plasma C5 level.
- All Cemdisiran Treated Set: All patients who received at least one dose of cemdisiran, including patients who took cemdisiran during the DB period and patients who first took placebo during the DB period and switched to cemdisiran during the OLE period.

The primary population used to evaluate efficacy will be the mITT Population unless stated otherwise. Safety during the DB period will be analyzed using the Safety Analysis Set. The PK and PD Analysis Sets will be used to conduct PK and PD analyses, respectively. The All Cemdisiran Treated Set will be used to summarize long-term efficacy and safety of cemdisiran.

4.2. **Protocol Deviations**

Protocol deviations will be classified into major or minor deviations by medical review. A major deviation is defined as a deviation that may significantly impact the completeness, accuracy and/or reliability of the trial data; that may significantly affect a patient's rights, safety and wellbeing (ICH.E3 R1 Structure and Contents of Clinical Study Reports Guidance for Industry. 2013). Major protocol deviations will be reviewed and approved by Alnylam prior to the interim database lock for the primary analysis of the DB treatment period. All protocol deviations will be presented in a listing. The Sponsor or designee will be responsible for producing the final protocol deviations file. This file will include at a minimum each protocol deviation and whether or not this deviation is classified as a major protocol deviations. This file will be finalized prior to the primary treatment phase database lock. Protocol deviations will be summarized in the CSR.

